3.6.5 Discontinuation of study treatment components

The reasons for discontinuation of each study treatment component will be summarized by treatment arm, based on the information on the component-specific DAR CRFs (i.e. using the “Reason Dose Permanently Discontinued” field on the applicable DAR CRF for patients who have the “dose permanently discontinued” box checked).

Partial discontinuation: Partial discontinuations and their reasons will also be summarized for ribociclib/placebo and goserelin (separately). Partial discontinuation refers to discontinuation of ribociclib/placebo or goserelin, respectively, while continuing on study treatment.

- For ribociclib/placebo, partial discontinuation is defined as the event when the last non-zero dose of ribociclib/placebo is more than 21 days before the last non-zero dose of study treatment, with the permanent discontinuation box checked in the ribociclib/placebo DAR page;
- For goserelin, partial discontinuation is defined as the last non-zero dose of goserelin plus 27 days being more than 21 days before the last non-zero dose of study treatment, with the permanent discontinuation box checked on the goserelin DAR page.

3.7 Concomitant and post treatment therapy

Concomitant therapy

Concomitant therapy is defined as all interventions (therapeutic treatments and procedures) besides the study treatment that were administered to a patient, coinciding with the study assessment period (even if started before the study assessment period).

Concomitant medications will be coded using the World Health Organization (WHO) Drug Reference Listing (DRL) dictionary that employs the WHO Anatomical Therapeutic Chemical (ATC) classification system.

Concomitant medications will be summarized by lowest ATC class, preferred term and treatment arm. These summaries will include:

1. medications starting on or after the start of study treatment but no later than 30 days after last dose of study treatment, and
2. medications starting prior to the start of study treatment and continuing after the start of study treatment.

All concomitant therapies will be listed. Any concomitant therapies starting and ending prior to the start of study treatment or starting more than 30 days after the last date of study treatment will be flagged in the listing.

[figure not shown]
The safety set will be used for all concomitant medication tables and listings.

Concomitant medications that have the potential to impact some specific analyses (e.g. PK, efficacy or safety analyses) will be identified prior to database lock. Separate summaries of these concomitant medications will be produced using the appropriate analysis set (e.g. FAS for those potentially affecting efficacy).

- Strong inhibitors or inducers of CYP3A4/5, substrates of CYP3A4/5 with a narrow therapeutic window, medications with a known risk of QT prolongation and other prohibited medications described in [Section 2.4](#) will be identified. They will be tabulated by ATC class and preferred term.
- Any anti-neoplastic therapy administered concomitantly with study treatment will be listed based on their identification through the protocol deviation process.

Post treatment anti-cancer therapy

Anti-neoplastic therapies after discontinuation of study drug will be listed and tabulated by ATC class, preferred term and treatment arm by means of frequency counts and percentages using the FAS. In addition, 1st and 2nd new anti-neoplastic medication regimens after discontinuation of study treatment will be summarized by medication type, e.g. hormonal therapy, chemotherapy, etc. The medication type will be determined by clinical review.

3.8 Efficacy evaluation

The efficacy endpoints based on the tumor assessments will be derived according to the RECIST guideline version 1.1 (see Section 2.5 and Appendix 3 of the Clinical Study Protocol for details). The tumor endpoint derivation is based on the sequence of overall lesion responses at each assessment/time point. However, the overall lesion response at a given assessment/time point may be provided from different sources as illustrated in [Table 3-2](#).

Table 3-2 Sources for overall lesion response

Source 1	Investigator (local radiology) reported overall lesion response
Source 2	Novartis-calculated overall lesion response based on raw (i.e. individual lesion) measurements from investigator (local radiology)
Source 3	Final BIRC-reported overall lesion response

The primary efficacy analysis will be based on the investigator/local radiology review. The investigator reported overall lesion response at each assessment/time point (Source 1 in [Table 3-2](#)) will be used to derive the efficacy endpoints.

The overall response at each assessment will also be calculated using the raw lesion measurements (Source 2 in [Table 3-2](#)). The calculated responses will be listed along with the responses given by the investigator. As a sensitivity analysis, PFS based on calculated overall lesion response (Source 2 in [Table 3-2](#)) will also be summarized.

Tumor assessment data based on BIRC assessment (Source 3) will be used for selected supportive efficacy analyses. The BIRC comprises of two independent radiologists and an adjudicator. The BIRC-reported overall lesion response data will be used to derive the BIRC-based endpoints. Data from independent readers will be listed together with the adjudication. . Differences in overall responses between local radiology (Source 1) and central radiology (Source 3) will be listed.

3.8.1 Primary efficacy

PFS based on local radiology assessment is the primary efficacy variable in this study. PFS is defined as the time from the date of randomization to the date of the first documented disease progression or death due to any cause. If a patient has not progressed or died at the analysis cutoff date, PFS will be censored at the time of the last adequate tumor assessment before the cut-off date. Definitions and further details on PFS can be found in Appendix 3 of the study protocol.

Discontinuation due to disease progression (collected on the ‘End of treatment’ and ‘End of post treatment follow up’ disposition page) without supporting objective evidence (as defined in [Section 2.5.2](#)) satisfying progression criteria per RECIST will not be considered disease progression for PFS derivation.

3.8.1.1 Primary analysis

The primary analysis of PFS will be based on the local radiological assessments (Source 1 in [Table 3-2](#)). The analysis will be performed on the FAS and will use the default censoring and event date options from Table 3-2 of study protocol Appendix 3 i.e. event/censoring rules will be based on options A(1), B(1), C1(1), C2(1), D(1), E(1), and F(1) (summarized in [Table 3-3](#)). In particular, PFS will be censored at the last adequate tumor assessment if a patient didn’t have an event or the event occurred after two or more missing tumor assessments (see [Section 2.5.5](#)). In the primary analysis in this study PFS will not be censored if a new antineoplastic therapy is started; instead, an ITT approach will be used and this new antineoplastic therapy will be ignored for the purposes of PFS derivation (and tumor assessments will continue), i.e. option F(1) in Table 3-2 of protocol Appendix 3 will be used. A sensitivity analysis will be performed censoring PFS at the last adequate tumor assessment prior to start of new antineoplastic therapy, i.e. using option F(2). Discontinuation of study treatment (for any reason) will not be considered as a reason for censoring.

Table 3-3 Outcome and event/censor dates for PFS analysis

Situation	Date	Outcome
-----------	------	---------

No baseline assessment	Date of randomization*	Censored
Progression or death at or before next scheduled assessment	Date of progression (or death)	Progressed
Progression or death after exactly one missing assessment	Date of progression (or death)	Progressed
Progression or death after two or more missing assessments	Date of last adequate assessment prior to missed assessments	Censored
No progression (or death)	Date of last adequate assessment	Censored
New anticancer therapy given prior to protocol defined progression	Ignore the new anticancer therapy and follow situations above	As per above situations
Treatment discontinuation due to 'Disease progression' without documented progression, i.e. clinical progression based on investigator claim	Ignore clinical progression and follow situations above	As per above situations
* The rare exception to this is if the patient dies no more than D2 days (see Section 2.5.5 for definition) after randomization, in which case this is a PFS event at the date of death		

3.8.1.2 Hypothesis and test statistic

The primary efficacy analysis will be the comparison of PFS between the two treatment arms using a stratified (strata based on IRT data) log-rank test at one-sided 2.5% level of significance.

Assuming proportional hazards model for PFS, the following statistical hypotheses will be tested to address the primary efficacy objective:

$$H_{01}: \theta_1 \geq 0 \text{ vs. } H_{a1}: \theta_1 < 0$$

where θ_1 is the log-hazard ratio (Tamoxifen or a NSAI+goserelin+ribociclib arm vs. tamoxifen or a NSAI+goserelin + placebo arm) of PFS.

3.8.1.3 Kaplan-Meier estimates

The survival distribution of PFS will be estimated using the Kaplan-Meier method. The results will be plotted graphically (Kaplan-Meier curves) by treatment arm. The plots will display the number of patients at risk at equidistant time points. The median, 25th and 75th percentiles for PFS for each treatment arm will be provided with associated 95% confidence intervals. The survival probabilities at 2-month intervals, and the associated 95% confidence intervals, will be summarized by treatment arm. Kaplan-Meier estimates will be obtained using PROC LIFETEST with method=KM option in SAS. The loglog option available within PROC LIFETEST will be used to compute the confidence intervals.

3.8.1.4 Hazard Ratio

The PFS hazard ratio with two-sided 95% confidence interval will be estimated using the stratified Cox proportional hazards model. In this analysis the baseline hazard function will be allowed to vary across strata. SAS PHREG procedure with ties=EXACT option will be used to carry out this analysis in which the model statement will include treatment arm variable as the

only covariate and the STRATA statement will include the stratum information as obtained via IRT.

3.8.1.5 Sensitivity and supportive analyses of the primary endpoint PFS

NSAI/tamoxifen subgroup analyses

In addition to the primary analysis in all patients, the treatment effect in terms of PFS for

1. tamoxifen + goserelin + ribociclib vs. tamoxifen + goserelin + placebo, and
2. NSAI + goserelin + ribociclib vs. NSAI + goserelin + placebo,

where tamoxifen/NSAI are identified based on CRF data, will be estimated using separate unstratified Cox regression models. Estimated hazard ratios with corresponding 95% CIs will be presented for each subgroup. Survival distribution of PFS will be estimated using Kaplan-Meier methodology within each subgroup.

Audit-based BIRC assessment of PFS

PFS assessed by Blinded Independent Review Committee (BIRC) will be used as a supportive analysis of the primary endpoint.

For studies with PFS based on local radiology assessment as the primary endpoint, PFS assessed centrally has generally been used as a secondary or supportive analysis of the treatment effect observed in the primary efficacy analysis. Although 100% central review of scans has been performed in many trials, there is a growing body of evidence that an audit based approach for central evaluation is sufficient ([Zhang et al, 2012](#), [FDA ODAC 2012](#)).

An audit (sample) based approach will therefore be implemented for the BIRC assessment of PFS, whereby all assessments for a randomly selected subset of randomized patients will be assessed by BIRC. An independent random sampling process, implemented by the third party IRT vendor, will select approximately 40% of randomized patients. This random allocation will be stratified by randomized treatment arm and the strata used for the randomization of patients to treatment arms.

The distribution of PFS based on the audit BIRC sample will be estimated using the Kaplan-Meier method. The median along with two-sided 95% confidence interval (CI) will be presented by treatment group. A Kaplan-Meier figure will also be displayed. A stratified Cox regression will be used to estimate the hazard ratio (HR), along with two-sided 95% CI based on the audit BIRC sample.

In order to determine whether a 100% BIRC review should be conducted, two additional methods will be used to summarize the data from the sample-based BIRC assessment.

1. NCI method: The NCI (National Cancer Institute) method ([Dodd et al. 2011](#)) uses an auxiliary variable estimator of the log-hazard ratio that combines information from patient-level investigator assessments from all patients (in the FAS) and the BIRC assessment of patients randomly selected for central review (see [Section 4.2.5](#) for methodology details). This estimate and its one-sided 95% CI will be provided. The NCI method is used for the audit sample size determination (see [Section 3.16](#)) and summary of treatment effect for the supportive BIRC assessment.

2. PhRMA method: The data from the BIRC assessment generated following the sampling scheme as above will also be summarized using the method proposed by [Amit et al. 2011](#), referred to as the PhRMA (Pharmaceutical Research and Manufacturers of America) method, based on the early discrepancy rate (EDR) and late discrepancy rate (LDR). The EDR quantifies the frequency with which the investigator declares progression early relative to BIRC within each arm as a proportion of the total number of investigator assessed PDs. The LDR quantifies the frequency that the investigator declares progression later than BIRC as a proportion of the total number of discrepancies within the arm (see [Section 4.2.5](#) for further details). If the distribution of discrepancies is similar between the arms this suggests the absence of evaluation bias favoring a particular arm. With this approach, the differential discordance (DD) of the early discrepancy rate (EDR) and late discrepancy rate (LDR) between the two arms will be estimated as the rate on the ribociclib arm minus the rate on the placebo arm. The EDR and LDR results will also be summarized by treatment arm.

The following thresholds based on the NCI and PhRMA methods will be used to define the trigger for a full BIRC review:

- If the upper-bound of the one-sided 95% confidence interval for BIRC-based log-hazard ratio exceeds zero (i.e. $HR > 1$) based on the NCI method
- and/or
- If $\geq 15\%$ differential discordance is observed in EDR or LDR based on the PhRMA method.

A full BIRC review will only be considered if the primary endpoint is statistically significant. In the event of a full BIRC read of all patients' imaging data, all analyses based on BIRC assessment will be repeated including all randomized patients, with the exception of the auxiliary variable estimate (NCI method) described above.

Sensitivity analyses and additional supportive analyses

As a sensitivity analysis to assess the impact of stratification, the two treatment groups will be compared using an unstratified log-rank test. The hazard ratio together with associated 95% confidence interval obtained using the unstratified Cox regression model will also be presented.

The primary efficacy analyses; i.e. the stratified log-rank test, Kaplan-Meier estimates, estimate of the median PFS along with 95% confidence interval, and hazard ratio obtained using the Cox proportional hazards model, will be repeated (as appropriate) based on the data obtained:

1. Using the investigator/local assessments (Source 1 in [Table 3-2](#)) on the PPS and using the same conventions as for the primary analysis if the primary analysis is found to be statistically significant and if the PPS/FAS are different.
2. Using investigator/local assessment (Source 1 in [Table 3-2](#)) on the FAS and taking the event whenever it occurs - even after two or more missing tumor assessments. The following options from Table 3-2 in Section 3.2.10 of Study Protocol Appendix 3 will be used: A(1), B(1), C1(1), C2(3), D(1), E(1) and F(1). In the summary table, this approach is referred as 'Actual event PFS analysis'

3. Using investigator/local assessment (Source 1 in [Table 3-2](#)) on the FAS and backdating events occurring after missing tumor assessments. The following options from Table 3-2 in Section 3.2.10 of Study Protocol Appendix 3 will be used: A(1), B(1), C1(2), C2(2), D(1), E(1), and F(1). In the summary tables, this approach is referred as 'Backdating PFS analysis'.
4. Using investigator/local assessment (Source 1 in [Table 3-2](#)) on the FAS and censoring PFS at the last adequate tumor assessment before the start of any new antineoplastic therapy (excluding palliative radiotherapy and continuation of combination partner therapy alone after end of study treatment).

A stratified multivariate Cox regression model will be fitted to evaluate the effect of other baseline demographic or disease characteristic on the estimated hazard ratio. This model will include treatment arm and the following key prognostic factors: ECOG performance status (0 vs. ≥ 1), bone only lesion at baseline (yes or no), age (<40 vs ≥ 40 years old), and prior (neo-)adjuvant hormonal therapy usage (no; yes – progression while on or within 12 months of end of (neo-)adjuvant ET; yes – progression > 12 months after end of (neo-)adjuvant ET). In addition, stratified multivariate Cox models will be fitted including treatment arm and each of these factors individually, including treatment by factor interaction, to explore the relationship between each factor and treatment.

Further supportive analyses will include:

- Stratified Cox regression using derived local radiology assessment (source 2 in [Table 3-2](#)). No p-value will be presented.
- Number of patients and number of events by treatment arm within each stratum and for each level of each stratification factor will be presented along with the hazard ratio for treatment effect obtained using unstratified Cox proportional hazards regression models with corresponding confidence intervals. No p-values will be presented for these analyses. K-M plots of survival distributions will also be presented.
- If there is a high rate of discrepancy between the strata classifications constructed using the eCRF data and those obtained from the IRT, a sensitivity analysis will be performed in which a stratified Cox regression model will be used to estimate the treatment hazard ratio and the associated 95% confidence interval based on the CRF-derived strata. No other inferential statistics will be provided.
- Number of patients with a PFS event and number of patients censored for the PFS analysis will be summarized. In addition, a summary of reasons for PFS censoring will be provided by treatment arm based on the reasons defined in [Section 2.5.5](#). These summaries on censoring reasons will be produced for PFS by investigator radiology and BIRC review.
- Comparison of PFS event type/censor between local radiology review and BIRC review
- 
- If more than 5% of the patients are found to have been force randomized, a sensitivity analysis using local radiology assessments (Source 1 in [Table 3-2](#)) will be performed on

all randomized patients with the force randomized patients assigned to the alternative treatment group.

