## 2.2 Rationale for the study design

This is a randomized, placebo-controlled two-arm study with the objective to evaluate the effect of adding LEE011 to tamoxifen and goserelin or a NSAI and goserelin in premenopausal patients with advanced breast cancer. The randomized, double-blind, placebo-controlled, multicenter, parallel group design is the gold standard design for phase III trials as it minimizes allocation bias, balancing both known and unknown prognostic factors in the assignment of treatments.

Randomization is stratified by the following factors:

1. Lung or liver metastases: (yes versus no)
2. Prior chemotherapy for advanced disease: (yes versus no)
3. Endocrine combination partner (tamoxifen and goserelin versus NSAI (letrozole or anastrozole) and goserelin)

The first two stratification factors are selected because of their well-recognized prognostic value and the third factor is selected to balance randomization within the two endocrine therapy groups.

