### **10.4.2 Statistical hypothesis, model, and method of analysis**

The primary efficacy analysis will be the comparison of PFS between the two treatment groups using a stratified log-rank test at one-sided 2.5% level of significance.

Assuming proportional hazards model for PFS, the following statistical hypotheses will be tested to address the primary efficacy objective:

$$H_{01}: \theta_1 \geq 0 \text{ vs. } H_{a1}: \theta_1 < 0$$

where  $\theta_1$  is the log-hazard ratio (Tamoxifen or a NSAI+goserelin+LEE011 arm vs. tamoxifen or a NSAI+goserelin + placebo arm) of PFS.

The primary efficacy endpoint PFS will be analyzed based on the FAS according to the treatment group patients were randomized and the strata they were assigned at randomization (strata formed using the randomization factor as obtained via IRT). PFS will be estimated using the Kaplan-Meier method. The median PFS along with 95% confidence intervals will be presented by treatment group. A stratified Cox regression model will be used to estimate the hazard ratio of PFS, along with 95% confidence interval. The primary analysis for PFS will be performed after approximately 329 PFS events have been documented per local assessment.

In addition to the primary analysis in all patients, the treatment effect in terms of PFS for

1. tamoxifen + goserelin + LEE011 vs. tamoxifen + goserelin + placebo, and
2. NSAI + goserelin + LEE011 vs. NSAI + goserelin + placebo

will be estimated using separate Cox regression models. Estimated hazard ratios with corresponding 95% CIs will be presented for each subgroup. PFS will be estimated using Kaplan-Meier methodology within each subgroup.

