In addition to the subgroup analyses for patients receiving tamoxifen and those receiving NSAI ([Section 10.4.2](#)), subgroup analyses will be performed on each level of stratification factors if the primary analysis is significant. The analysis will include Kaplan-Meier summaries and estimation of hazard ratios from un-stratified Cox regression models. Additional subgroup analyses to assess the homogeneity of treatment effect based on demographic and baseline disease characteristics may be performed; details about the subgroups to be included will be provided in the study analysis plan.

Patterns of censored data will be examined by the treatment groups using descriptive statistics (the numbers of censored patients and reasons for censoring).

Since the primary endpoint of PFS was met at the time of the primary analysis, no further formal analyses of PFS are planned. If any descriptive analyses of PFS are performed after allowing patients ongoing on study treatment in the placebo arm to crossover to the LEE011 combination arm (permitted after the study had met its primary and key secondary endpoints), appropriate sensitivity analyses will be considered and described in the SAP, for example censoring PFS at the last adequate tumor assessment prior to crossover for patients in the crossover analysis set.

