3.2.1 Basic demographic and background data

Demographic and background disease characteristics data will be listed in detail. Qualitative data (e.g. race, ECOG performance status, etc.) will be summarized by means of contingency tables by treatment arm and quantitative data (e.g. age, body weight, etc) will be summarized by appropriate descriptive statistics (mean, standard deviation, median, minimum, and maximum) by treatment arm.

Discrepancies between randomization stratification information (obtained from the Interactive Response Technology (IRT) system) and stratum information based on data collected on CRFs will be tabulated and listed.

Unless otherwise specified, stratified analyses and analyses “by stratum” will be based on IRT stratification data, while data for other subgroup analyses and model covariates will be based on CRF data.

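### Are the tamoxifen and NSAI subgroup PFS hazard ratios misleading because their Cox models leave out two prognostic randomisation factors?

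*SAP*

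**What the plan says.** The primary PFS hazard ratio is "estimated using the stratified Cox proportional hazards model", and "the STRATA statement will include the stratum information as obtained via IRT" (SAP 3.8.1.4). The test statistic in SAP 4.2.3 uses eight strata.

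For the two endocrine-partner comparisons, SAP 3.8.1.5 says the treatment effects "will be estimated using separate unstratified Cox regression models", with the partner taken from the CRF. Protocol 10.4.2 says only that these effects "will be estimated using separate Cox regression models", without stating whether the models are stratified.

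Three other places bear on this:

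- Protocol 10.4.4 prescribes unstratified Cox models for the subgroup analyses by level of each stratification factor. SAP 3.8.1.5, under further supportive analyses, does the same. Endocrine partner is one of those factors.
- SAP 3.8.1.5 compares the whole population without strata as a sensitivity analysis, and the hazard ratio "obtained using the unstratified Cox regression model will also be presented".
- Protocol 2.2 gives the reasons for the factors: "The first two stratification factors are selected because of their well-recognized prognostic value". The third, endocrine partner, was chosen for balance.

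**The concern.** Within a tamoxifen or NSAI subgroup the partner is essentially constant, so an unstratified model drops exactly the two factors chosen for prognosis. Leaving a prognostic factor out of a Cox model moves the expected hazard ratio towards 1, even under perfect randomisation, because a marginal hazard ratio differs from a within-stratum one.

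The two subgroup results will be read next to the stratified primary hazard ratio. A reader could take part of the gap for a weaker effect with one partner when it comes from the choice of model. The model-based standard error also takes no account of the stratified randomisation. If the distortion were large, the account of benefit by endocrine partner would be wrong.

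**Working it through.** **1. The plan's own figure.** SAP 3.16: hazard ratio 0.67, one-sided 2.5%, 95% power, 1:1 allocation, 329 events. Schoenfeld's formula gives 4 × (1.960 + 1.645)² / (ln 0.67)² = 51.98 / 0.1604 = 324.1, so 325 events; Freedman's gives 333. Power at 329 events is Φ(√329 × 0.4005 / 2 − 1.960) = Φ(1.67) = 95.3%. The design figure reproduces, so 0.67 is a sound reference value.

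**2. Inputs for the attenuation.** From the plan: hazard ratio 0.67, control median PFS 9 months, cut-off about 22 months. The documents give no subgroup sizes, factor prevalences or prognostic effects. Assumed: subgroups of 180 and 480; 50% with lung or liver metastases; 15% with prior chemotherapy; prognostic hazard ratios of 1.5/1.3, 2.0/1.5 and 2.5/2.0 for the two factors; exponential PFS; uniform censoring from 4 to 22 months; permuted blocks of 4 within the four strata. This yields about 96 and 255 events.

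**3. Mean hazard ratio (10,000 replicates per scenario).**

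| n | 1.5/1.3 | 2.0/1.5 | 2.5/2.0 |
|---|---|---|---|
| 180, unstratified | 0.671 | 0.684 | 0.694 |
| 480, unstratified | 0.674 | 0.684 | 0.695 |

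The stratified model gives 0.665 to 0.670 throughout. Large-sample limits under a range of assumed effects agree: 0.673 (both factors 1.25) to 0.699 (2.5 and 2.0, with 30% prior chemotherapy), and 0.715 at an extreme of 3.0 for both. If the factors have no prognostic effect, there is no shift.

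**4. Shift against sampling error.** The standard error of the log hazard ratio is about 2/√events: 2/√96 = 0.204 and 2/√255 = 0.125. In the middle scenario the shift is ln(0.684/0.67) = 0.021, about 10% of a standard error at n=180. In the strongest it is ln(0.695/0.67) = 0.037, about 29% at n=480. In a single trial of 165 to 495 patients with milder or similar factor effects, the unstratified estimate was the closer to 1 in only 56% to 70% of simulations.

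**5. Accuracy around 0.67.** Root mean squared error of the log hazard ratio, same assumptions, 4,000 replicates per scenario:

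| n | Model | 1.5/1.3 | 2.0/1.5 | 2.5/2.0 |
|---|---|---|---|---|
| 180 | unstratified | 0.202 | 0.203 | 0.201 |
| 180 | stratified | 0.209 | 0.215 | 0.215 |
| 480 | unstratified | 0.125 | 0.125 | 0.124 |
| 480 | stratified | 0.128 | 0.130 | 0.128 |

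The planned model has the smaller error in all six. Coverage of 0.67 by the 95% interval is 94.9% to 95.8% unstratified and 94.6% to 95.2% stratified.

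**6. Signal to noise, hardest case (n=480, 2.5/2.0).** The unstratified SD is √(0.124² − 0.037²) = 0.118, so signal to noise is |ln 0.695| / 0.118 = 0.364 / 0.118 = 3.1. For the stratified model, almost unbiased, it is 0.400 / 0.128 = 3.1. Stratifying enlarges the estimate and its spread together.

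**7. Standard error.** Mean model standard error over true SD is 1.00 to 1.07 unstratified and 0.99 to 1.01 stratified. The unstratified interval therefore errs, if at all, on the conservative side. The stratified interval is wider by 1.5% to 2.1% at n=180 and by 0.6% to 1.0% at n=480.

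**The case for a change.** The best argument for stratifying starts from the text. Protocol 10.4.2 leaves the model open, and the unstratified rule in 10.4.4 covers analyses introduced by "In addition to the subgroup analyses for patients receiving tamoxifen and those receiving NSAI", so it does not strictly govern these two. The comparisons are prominent: they stand in the protocol summary and beside the primary analysis. The SAP also stratifies other supportive hazard ratios, including the one from the 40% central-review audit sample, so small strata did not deter it. By SAP 3.2.1, stratified analyses "will be based on IRT stratification data", so the strata are at hand. And the 95% interval excludes 1 more often when stratified: 48.9% against 48.4%, 47.3% against 43.9% and 48.1% against 41.6% at n=180; 89.4% against 89.0%, 88.9% against 86.8% and 88.2% against 83.5% at n=480.

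What stands is that the protocol permits either model, that the average attenuation exists, and that the unstratified interval is somewhat conservative when the factors are strong. The rest carries less weight:

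- The larger gains need prognostic effects that the documents do not support with any figure, and they concern how often an interval excludes 1 for results that enter no test.
- A stratified subgroup value would still not be a clean reading against the primary hazard ratio, because a true difference between partners moves it either way.
- The by-level analyses already give unstratified tamoxifen and NSAI hazard ratios. At present the two pairs differ only in whether the partner comes from the CRF or from IRT. With different models, a gap between them could no longer be put down to the data source.
- At n=180 the two prior-chemotherapy strata would hold about 180 × 0.15 × 0.5 = 13.5 patients each and add little information.

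**Conclusion.** The planned models are sound. They estimate a marginal hazard ratio in each endocrine-partner subgroup, follow the convention the plan uses for its by-level subgroup hazard ratios, and have a like-for-like overall comparator in the unstratified sensitivity analysis. The expected shift from 0.67 is at most about 0.03 on the hazard-ratio scale under the assumed prognostic effects of 1.5/1.3 to 2.5/2.0, and 0.045 in the extreme case (0.715 − 0.67). It is smaller than the sampling error in every case simulated for subgroups of 165 to 495 patients. Stratifying would trade that shift for more variance, with no better coverage.

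The size rests on assumed subgroup sizes, prevalences and prognostic effects, since the documents give none. The classification does not: the choice is between two valid estimators, the results are supportive estimates only, and the primary PFS test, its hazard ratio and the hierarchical test of overall survival are the same under either. Nothing the trial can conclude depends on it.
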